# Sessions 1 (after baseline) and 2 will occur at the ACTRI and will take approximately 1 hour each to complete.

## Participant Randomization:

The schedule of randomization will be created and accessed by an ACTRI pharmacist only. Males and females will be randomized without replacement across a block of 20 codes (assuming 20% attrition) using an Excel-based random number generator. All subjects will receive OT in one session and saline placebo in the other in this within-subject cross-over study. Subjects will be randomized to one of two session orders (Session 1 OT and Session 2 saline; Session 1 saline and Session 2 OT). Randomization will be stratified so that each sex will have their respective list of randomization codes. Session order (blinded code) will be tracked in the Screening/Enrollment Log maintained by the study coordinator(s) and identity of the orders will be revealed by the pharmacy at the conclusion of the study.

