# Sample Size Determination & Power

We expect that pleasantness ratings of C-LTMR-optimal touch will be significantly increased after local OT injection and that pain perception will be reduced. In published studies, differences in postsurgical pain after local infiltration with OT versus control resulted in very large mean differences in VAS pain ratings of Cohen's d = 3 to 4.5. In spinal nerve ligation (SNL) model rats, interplantar injection of OT versus control resulted in mean differences in paw withdrawal threshold of Cohen's  $d = 13.8^{19}$ . In addition, intranasal oxytocin (24IU) increases pleasantness of touch stimuli (especially driven by negative stimuli), with an estimated Cohen's d of  $\sim 3^{23}$ . Although these are very large effect sizes, accounting for sampling variability and differences in proposed study design (acute pain; healthy adults; subcutaneous OT administration), we powered the study to detect a large effect size of d = 0.8. Assuming a within-subject correlation of 0.5 and an attrition rate of 25%,

the proposed sample size of N = 20 will provide 0.8 power to detect an effect size as small as d = 0.8 based on a two-sided  $\alpha = 0.05$ .

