## **Data Analyses and Interpretation**

General Statistical Approaches. Data will be analyzed descriptively and analytically. Descriptive statistics (means and standard deviations for continuous and proportions/counts for categorical outcomes) will be used to describe outcomes at baseline. Weighted generalized estimating equations (WGEE) will be employed, with appropriate link functions depending on the type of the response (e.g., identity for continuous and logit for binary outcome), to examine longitudinal changes in an outcome and longitudinal association between outcomes in regression analysis, controlling for covariates for Aims 1-2. Unlike parametric models such as generalized linear mixed-effects models (GLMM), the semi-parametric WGEE requires no distribution assumption and yields valid inference for a broader class of data distribution under the missing at random mechanism^123. WGEE provides valid inferences under the missing at random (MAR) mechanism^124. We will use WGEE to test the missing completely at random (MCAR) assumption and will use the generalized estimating equations (GEE), if the MCAR is not rejected. GEE involves fewer parameters and provides more efficient inference than WGEE. Given the small sample size for Aims 1-2, we will complement the usual asymptotic inference with clustered bootstrap to improve inference validity and report the bootstrap inference if it differs from its asymptotic counterpart. We set  $\alpha$ =0.05 for all analyses and use Holm-Bonferroni adjustments for <= 5 tests and False Discovery Rate (FDR) for > 5 tests. When correlated outcomes are analyzed (e.g., outcomes in related domains), corrections will be calculated based on the effective number of independent tests that account for correlations between the outcomes. Whenever possible, effect size will be reported in addition to point and interval estimates. All analyses will be performed using the latest versions of R^129 and SAS. Hypothesis Testing. For Aim 1, separately for OT and saline placebo sessions, we will compare changes in ratings of pain over time between the OT and control arm using WGEE, where time (one binary indicator) will be the predictor, controlling for covariates. A significant time effect, tested using appropriate linear contrasts, will support the hypothesis that the OT injection has effects on the outcome. We will follow with *post hoc* analyses to estimate the effect size of the OT injection. For Aim 2, we will apply the same approach in Aim 1 to pleasant touch outcome. Age and race/ethnicity will be included as potential covariates in all analyses.

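### The analysis compares raw pre-to-post changes without adjusting for the pre-injection value, which can cost up to a two-fold variance, depending on a pre-post correlation that the plan does not give

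*Combined protocol and SAP*

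**What the plan says.** In the combined protocol and SAP, section 9, Data Analyses and Interpretation, the Aim 1 analysis is run separately for the oxytocin and the saline session: "we will compare changes in ratings of pain over time between the OT and control arm using WGEE". The control arm is the forearm that was not injected (Post-sensory testing). A binary time indicator is the only predictor named. For touch: "For Aim 2, we will apply the same approach in Aim 1 to pleasant touch outcome".

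Age and race/ethnicity are the covariates named for all analyses. Elsewhere the protocol adds recorded behaviours such as caffeine and sleep. No section lists the pre-injection value as a covariate, although the touch and pain measures are taken before the injection in both sessions (Pre-sensory testing).

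The Sample Size section gives a single correlation, "Assuming a within-subject correlation of 0.5 and an attrition rate of 25" per cent, and concludes that "the proposed sample size of N = 20 will provide 0.8 power to detect an effect size as small as d = 0.8". It does not say which pair of measurements the correlation describes. Both aims are worded as oxytocin against saline, and session order is what is randomized.

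**The concern.** Subtracting the pre-injection value removes what it shares with the post-injection value, but it also adds all of its own measurement noise. Touch ratings rest on two trials per brushing speed and forearm, and heat ratings on three, so that noise may be large. Using the same value as a covariate removes only the part that predicts the outcome. With about 15 completers expected, the choice between the two could decide whether the effect size that the study was planned for is detected. The data needed for the better choice are already collected.

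**Working it through.** **Inputs from the documents.** N = 20, attrition 25%, correlation 0.5, d = 0.8, two-sided alpha 0.05 (Sample Size section; Data Analyses and Interpretation). Completers: 20 × 0.75 = 15.

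**Assumptions.** A single rating has SD 1. The correlation between sessions is 0.5. The pre-post correlation within a session and forearm, w, is not given, so I vary it from 0.5 to 0.9.

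**1. The plan's own figure.** A single paired difference has variance 2(1 − 0.5) = 1, so the standardized effect is 0.8/1 = 0.8. The paired t-test with 15 completers has power 0.82 (0.79 with 14), and 15/0.75 = 20. The stated figure reproduces, as a single paired difference. A difference of changes is a different quantity.

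**2. General formula.** Let the pre-injection and the post-injection difference each have variance V, with correlation r.
- Change-score contrast: 2V(1 − r).
- Adjusted contrast: V(1 − r²).
- Ratio: 2/(1 + r).

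For r ≥ 0 the ceiling is 2. The ratio is 1.6 at r = 0.25, 1.33 at 0.5 and 1.18 at 0.7.

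**3. The contrast as written (forearm against forearm in one session).** If every pair of measurements correlates at 0.5, the forearm difference after injection has variance 1, the difference of changes has variance 4(1 − 0.5) = 2, and r = 0. The ratio is 2. At variance 2, power for d = 0.8 with 15 completers is 0.53. Reaching 80% would take 27 completers, or 27/0.75 = 36 enrolled.

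**4. Oxytocin against saline, injected forearm.** Here V = 1 and r = (w − 0.5)/(1 − 0.5) = 2w − 1. The power of the adjusted analysis includes the cost of estimating the slope: a variance factor (15 − 2)/(15 − 1 − 2) = 13/12 = 1.08, and one degree of freedom.

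| w | r | variance, change | variance, adjusted | ratio | power, change | power, adjusted |
|---|---|---|---|---|---|---|
| 0.5 | 0 | 2.00 | 1.00 | 2.00 | 0.53 | 0.79 |
| 0.6 | 0.2 | 1.60 | 0.96 | 1.67 | 0.63 | 0.80 |
| 0.7 | 0.4 | 1.20 | 0.84 | 1.43 | 0.75 | 0.85 |
| 0.8 | 0.6 | 0.80 | 0.64 | 1.25 | 0.90 | 0.93 |
| 0.9 | 0.8 | 0.40 | 0.36 | 1.11 | about 1.00 | about 1.00 |

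At w = 0.9 the ratio net of the slope cost is 1.11/1.08 = 1.03, so nothing material is left. Simulation gave the same picture, with type I error near 5% for all the estimators.

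**5. Keeping the control forearm.** Take the injected-minus-control difference as the outcome and compare it between sessions. With all correlations 0.5, the post-injection contrast has variance 4(1 − 0.5) = 2 and the change version 8(1 − 0.5) = 4. The ratio is again 2. Simulated power with 15 completers is about 0.30 for changes and 0.49 adjusted. At w = 0.8, with the shared variance above 0.5 split equally between session and forearm-within-session (an assumption), it is 0.62 and 0.74.

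**The case against.** Several points on the other side are sound.

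- **A four-fold loss.** A reader might infer that the variance is quadrupled. The documents do not support that. The plan analyses the sessions separately and never writes a contrast that subtracts one session's forearm change difference from the other's. Even for that contrast, 4 is the product of two factors of 2: subtracting the baseline, and subtracting the control forearm. It appears only against an analysis of the injected forearm alone, which has a different target. For the same target the ceiling stays at 2.
- **Most of the cross-over advantage lost.** This might also be inferred, but it is too strong for a two-fold variance. At correlation 0.5 with N participants, a parallel-group comparison of post values has variance 4/N, the cross-over 1/N and the cross-over in changes 2/N. Change scores keep (4 − 2)/(4 − 1) = two thirds of the reduction.
- **Where the gain arises.** At w = 0.5 the pre-injection difference predicts nothing. A post-only paired comparison (0.82) then slightly beats the adjusted one (0.79), so the gain there comes from not subtracting. This stands. Adjustment is still the safer choice while w is unknown, because it stays close to the better of the two simple options over the range: 0.93 at w = 0.8, against 0.82 for post-only and 0.90 for changes.
- **Subtraction is not fully fixed by the text.** With time as the only predictor and no working correlation stated, a GEE with a common baseline mean could behave like adjustment. This stands, and it is a reason to write the model out.
- **Adjustment within one session has less support.** The control forearm is the comparator there, and the protocol does not describe randomizing which forearm is injected. The fix therefore belongs in the comparison between sessions.
- **No validity problem.** Correct: the issue is efficiency.

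**Conclusion.** The concern holds as an efficiency point. The plan compares raw changes and leaves the collected pre-injection value out of its covariates. For a change-score contrast this can inflate the variance by up to a factor of 2. The ceiling assumes that the plan's 0.5 also describes pre-post pairs; the documents give no such figure. The power loss for d = 0.8 on the injected forearm is then about 26 points (0.53 against 0.79). It falls to about 3 points at a pre-post correlation of 0.8 and to about nil at 0.9. The stated power of 0.8 is not disputed here; it reproduces for the single paired difference on which it rests.

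**What to change.** Add one paragraph to Data Analyses and Interpretation, for the oxytocin-versus-saline comparison in which session order is randomized:

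- Outcome: the post-injection value.
- Fixed effects: treatment (oxytocin or saline) and session.
- A participant effect.
- Covariates: the same-session pre-injection value and the participant's mean pre-injection value, in place of subtraction.

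To keep the question about a local effect, take as outcome the injected-minus-control forearm difference after injection, adjusted for the matching difference before injection. Analysing the injected forearm alone gives higher power in most of the range examined, but it estimates local plus any systemic effect. That changes the estimand and is a separate choice for the sponsor.

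The cost is one or two degrees of freedom and no new data. If the pre-injection values predict nothing, power falls by about 3 to 4 points against a post-only paired comparison (0.82 to 0.79 with 15 completers).

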#### 6. SPECIFIC AIMS

#### Aim 1: Assess whether subcutaneous injection of oxytocin versus saline placebo has local antinociceptive effects on experimental pain.

**Hypotheses:** We hypothesize that OT will reduce pain threshold and ratings of pain intensity and unpleasantness for thermal, mechanical, and pressure pain.

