# Aim 2. Assess whether subcutaneous injection of OT versus saline placebo alters local pleasantness of CT gentle stroking.

**Hypotheses:** We hypothesize that OT will increase touch pleasantness of slow versus fast stroking and will increase heart rate variability.

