Blood pressure and oxygenation will be monitored before and after OT injection and at approximately 5 minute intervals (BP) or continuously (pulse ox) for the remainder of the session.

**Post-sensory testing:** Perception of pain and gentle brushing will be tested beginning ~10min after injection on the injected arm, given timing of OT effects in prior studies, and then on the control arm. A post-block baseline sensory test will be conducted, identical to the affective sensory testing described above. All testing will be conducted within a ~3-4cm^2 sized region of skin proximate to the injection site on the dorsal forearm. At the end of testing, the injected arm will be observed by a licensed provider to confirm normal sensation and lack of any adverse response to OT injection.

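### The analysis tests change over time within each session and credits it to oxytocin; no oxytocin-versus-saline test is specified

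*Combined protocol and SAP*

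**What the plan says.** Section 6 states Aim 1 as whether "subcutaneous injection of oxytocin versus saline placebo has local antinociceptive effects on experimental pain", and Aim 2 is likewise worded against saline placebo. Participant Randomization (section 9) describes a two-session crossover in which each participant receives both injections in random order.

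The Hypothesis Testing text in Data Analyses and Interpretation is the only place where the tests are described. It says that "separately for OT and saline placebo sessions, we will compare changes in ratings of pain over time between the OT and control arm". The method is a weighted GEE, and the plan describes the model in these words: "where time (one binary indicator) will be the predictor, controlling for covariates". The decision rule is: "A significant time effect, tested using appropriate linear contrasts, will support the hypothesis that the OT injection has effects on the outcome". Aim 2 inherits it: "For Aim 2, we will apply the same approach in Aim 1 to pleasant touch outcome". A post hoc estimate of the size of the OT effect is promised, without a defined contrast.

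The named covariates are age and race/ethnicity. Behavioural covariates and sex appear elsewhere. None of these is a treatment term.

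The post-sensory testing text says that perception is "tested beginning ~10min after injection on the injected arm", given the timing in prior studies, "and then on the control arm". There, the control arm is the non-injected forearm.

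**The concern.** A pre-to-post change in the OT session mixes the drug with everything else that happens in that session: the 2 ml injection, repeated noxious testing, habituation or sensitisation, and expectancy. The saline session exists to remove these, but the plan never contrasts the two sessions. Linear contrasts inside two separate session models cannot supply that comparison.

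The reference to a control arm does not close the gap. Because the sessions are analysed separately, each analysis contains one drug only, so within it the comparison can only be between limbs, and no limb term is named. A limb comparison would cancel changes shared by both forearms. It would not separate OT from the injection itself, or from testing the injected limb first.

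The rule can therefore credit OT with a change that saline produces equally, or miss a real effect hidden by an opposite drift. The comparison that the randomisation was built to deliver is left to an informal reading of two p-values.

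A smaller mismatch sits alongside. The Aim 2 hypothesis is that "OT will increase touch pleasantness of slow versus fast stroking", whereas Outcome Measure(s) makes slow brushing the primary touch outcome. No velocity term is named.

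**Working it through.** **Inputs from the documents.** N = 20, d = 0.8, within-subject correlation 0.5, attrition 25%, power 0.8, two-sided alpha 0.05 (Sample Size Determination & Power). Holm adjustment for up to five tests (Data Analyses and Interpretation).

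**Inputs assumed.** A pre-to-post shift g of 0.3, 0.5 or 0.8 SD of change on the injected limb, equal in both sessions; no OT effect unless stated; correlation 0.3 between the limbs' changes and between the sessions' changes, varied below. Paired t-tests stand in for GEE.

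**1. The plan's own figure.** For one paired contrast, dz = d/√(2(1 − ρ)) = 0.8/√(2 × 0.5) = 0.80. Noncentral-t power is 0.790 at n = 14 and 0.821 at n = 15. Then 15/0.75 = 20. The stated N reproduces as a single two-condition paired contrast, but the text does not say which one.

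**2. False credit under the time-only rule.** n = 15, 14 df, critical t 2.145, noncentrality g√15. At the Holm first step for two primary tests (alpha 0.025), the critical t is 2.510.

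| g | g√15 | alpha 0.05 | alpha 0.025 |
|---|---|---|---|
| 0.3 | 1.16 | 0.192 | 0.119 |
| 0.5 | 1.94 | 0.438 | 0.317 |
| 0.8 | 3.10 | 0.821 | 0.717 |

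**3. False credit under a limb rule.** The SD of the difference between limb changes is √(2(1 − 0.3)) = 1.183. The effect left after subtraction is 0, g/2 or g, according to how much of the shift the control limb shares.

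| g | full shift shared | half shared | none shared |
|---|---|---|---|
| 0.3 | 0.050 | 0.074 | 0.150 |
| 0.5 | 0.050 | 0.119 | 0.332 |
| 0.8 | 0.050 | 0.231 | 0.683 |

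Over limb correlations from 0 to 0.7, the half-shared column ranges over 0.067–0.108, 0.098–0.214 and 0.175–0.461.

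**4. Reading significance under OT but not under saline as an OT effect.** The plan does not state this rule, but separate session analyses invite it. With independent session changes the error is p(1 − p): 0.192 × 0.808 = 0.155, 0.438 × 0.562 = 0.246 and 0.821 × 0.179 = 0.147. At correlation 0.3, simulation gives 0.13, 0.20 and 0.13; at 0.7, 0.09, 0.13 and 0.08. A direct test of the OT-minus-saline difference in change stays at 0.05 in every case.

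**5. Missed effects.** With a true OT effect of 0.8 SD of change and an opposite drift of 0.3 or 0.5, the net shift is 0.5 or 0.3. The time-only rule's power falls from 0.821 to 0.438 or 0.192.

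**6. Power of the alternatives.** d = 0.8, 15 completers, 0.5 taken as the common correlation among all ratings.

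- Baseline-adjusted drug contrast, injected forearm (40,000 simulated trials): 0.788 without and about 0.77 to 0.78 with a period term. With period at alpha 0.025, about 0.66. Under no effect it rejects at about 0.05.
- Change-score drug contrast, or drug × velocity or drug × limb on post-injection values with the full effect in one cell: variance 4(1 − 0.5) = 2, dz = 0.8/√2 = 0.566, power 0.532. For 80% power: 27 completers, 27/0.75 = 36 enrolled.
- Drug × limb on change scores: variance 8(1 − 0.5) = 4, dz = 0.8/√4 = 0.40, power 0.303; 52 completers, 52/0.75 = 69.3, so 70 enrolled.

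The 27 depends on the correlation: common values of 0.3, 0.5, 0.7 and 0.8 give 37, 27, 17 and 12 completers (50, 36, 23 and 16 enrolled).

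**The case against.** The strongest reply is that the investigators plainly intend to compare OT with saline. The aims and the opening of section 9 say so, the saline session is analysed, and the control-arm wording may mean the saline treatment arm, with the word for separate analysis a drafting slip. It is true that a saline session has no OT arm, so the limb reading does not fit both sessions cleanly. But if saline was meant, the sentence contradicts itself, and on neither reading does the named model contain a term that carries the comparison. Intent is not in doubt; the specified test does not deliver it. The post hoc effect estimate does not help, because its contrast is undefined too.

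A second reply is that the 19/44/82% figures take the harshest reading and assume the shift. That is fair as to size. Under a limb rule with the shift fully shared, the error is 5%. The figures illustrate the rule and do not estimate this trial's error rate. The direction does not depend on the value chosen: under the time-only rule, any non-zero shift common to both sessions pushes the error above 5%.

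A third reply is that the repair costs power. This stands in part. The recommended model falls slightly below the stated 0.80 under a common correlation of 0.5, and further at a Holm first step. The penalty for change scores shrinks if ratings correlate more strongly within a session: at 0.8 within and 0.5 between sessions, the change-score contrast has about 0.89 power and the baseline-adjusted contrast about 0.93.

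**Conclusion.** The concern holds. As written, the confirmatory rule tests neither aim: it reads a within-session change as an OT effect and leaves the randomised comparison untested. With 15 completers and an assumed common shift of 0.3 to 0.8 SD of change, the chance of falsely crediting OT is 19% to 82% under the time-only rule, and from 5% up to 68% under a limb rule, depending on how far the control limb shares the shift. These sizes rest on assumed shifts and correlations. The defect itself rests only on the plan's text. It lies in the analysis specification; the sample-size arithmetic is sound for one paired contrast. It should be corrected before the session orders are revealed. The slow-versus-fast mismatch is a minor addition.

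**What to change.** Replace the Hypothesis Testing rule with one model over both sessions, for example:

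> *Post-injection values on the injected forearm from the OT and saline sessions will be modelled together, clustered by participant, with drug (OT or saline), period and the same session's pre-injection value as predictors. The drug contrast is the test of OT versus saline for the primary pinprick outcome (Aim 1) and for slow-brush pleasantness (Aim 2).*

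Also:

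- Name the single pinprick variable meant. The pain perception procedures give a threshold, single-stimulus ratings and ten-repetition ratings.
- Keep within-session time effects descriptive, and define the post hoc effect size as the drug contrast.
- State that the control arm is the non-injected forearm, and report drug × limb as supportive evidence that an effect is local.
- For Aim 2, either add drug × velocity as the test of the slow-versus-fast hypothesis or reword that hypothesis to match the primary outcome.
- Restate power for the contrast chosen, with its correlation assumption and the multiplicity step.

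The cost is SAP wording and a new power paragraph; the drug contrast needs no new data or visits. The power statement will be less favourable: about 0.77 at 0.05 and 0.66 at 0.025 for the recommended model with 15 completers and a common correlation of 0.5. Making drug × velocity, or drug × limb on post-injection values, confirmatory would need about 27 completers (36 enrolled) under the same assumption, so label these supportive unless the sample is enlarged.

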# Heat pain calibration

Ratings of heat stimuli will be collected to determine a moderately painful heat stimulus for use in pre- and post-sensory testing. Ascending and descending series of 10s heat stimuli (32-50°C) will be presented on the arm until pain intensity is rated '70' on the visual analog scale (VAS) pain intensity scale.

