
## **10. HUMAN SUBJECTS**

## **Subject Population**

A total of 20 healthy adults, ages 18-65, will complete two separate test sessions in a within-subject crossover study. Equal numbers of males and females will be recruited. Data will be analyzed to determine if sex is a significant predictor of study outcomes. We will include all genders, races, and ethnicities.

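### No planned model includes session number, although the trial is a two-session crossover whose aims compare oxytocin with saline; the term should act on pre-post change in one pooled model

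*Combined protocol and SAP*

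**What the plan says.** Under Participant Randomization, "Subjects will be randomized to one of two session orders (Session 1 OT and Session 2 saline; Session 1 saline and Session 2 OT"). The same section adds: "Randomization will be stratified so that each sex will have their respective list of randomization codes". Section 6 frames both aims as OT versus saline placebo.

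Data Analyses and Interpretation describes the Aim 1 test: "separately for OT and saline placebo sessions, we will compare changes in ratings of pain over time between the OT and control arm", "where time (one binary indicator) will be the predictor, controlling for covariates". A significant time effect is taken as support for an OT effect, and Aim 2 follows the same approach. On adjustment it says: "Age and race/ethnicity will be included as potential covariates in all analyses". The sections on baseline measures and exclusion criteria add diet, sleep, exercise and similar behaviours as covariates. Session number, period and order appear in no model. Sex is absent from this section, but Subject Population says: "Data will be analyzed to determine if sex is a significant predictor of study outcomes".

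On heat calibration: "Ratings of heat stimuli will be collected to determine a moderately painful heat stimulus for use in pre- and post-sensory testing". Consent is taken at the start of Session 1, baseline measures follow consent, and Session 1 testing is described as coming after baseline.

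**The concern.** In a two-period crossover, each treatment's data mix first and second sessions. If ratings respond differently in the two sessions, that difference is either spread through the residual (orders equal) or partly attributed to treatment (orders unequal). The usual protection is a period term. Age and race/ethnicity do not vary within a person, so they do not do this job.

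A session difference is plausible here. Session 1 testing appears to follow about 30 minutes of baseline measures and a series of 32-50 °C stimuli taken up to a pain rating of 70. Session 2 has no calibration, and by then participants have had one injection and the whole test battery. At stake are power, and some bias if dropout leaves the orders unequal.

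**Working it through.** **1. The plan's own figure.** Sample Size Determination gives N = 20, d = 0.8, within-subject correlation 0.5, 25% attrition and two-sided alpha 0.05. The standardised paired effect is 0.8/√(2(1 − 0.5)) = 0.8. The smallest number of completers with paired-t power of at least 0.80 is 15 (power 0.821), and 15/0.75 = 20. The figure reproduces as a paired, cross-session contrast. (Participant Randomization assumes 20% attrition; 25% is used here.)

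**2. Which session effects survive.** Take a 0.5 SD shift in Session 2.
- A shift in rating level, before and after injection alike, cancels in pre-post change: bias 0.
- A shift in the change, common to both forearms, cancels in a forearm-by-time contrast but not in a time effect. In the OT session at 8:7, 7 of 15 participants are in Session 2, so the time effect moves by 0.5 × 7/15 = 0.233. It also remains in an OT-minus-saline contrast of change.
- A shift in the change of one forearm only survives in all of these. The calibration section does not say which arm is heated.

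**3. Cost to an OT-versus-saline contrast of change.** Let D be OT minus saline with SD 1, τ = 0.8 the true effect, π the session effect, and n₁ and n₂ the numbers with OT first and second. Then E[D] = τ − π (OT first) or τ + π (OT second).
- Unadjusted: one-sample t on D. Bias = π(n₂ − n₁)/n. The expected sample variance is 1 + 4π²n₁n₂/(n(n − 1)). At 8:7 and π = 0.5 this is 1 + 0.25 × 224/210 = 1.267, so the standard error is multiplied by 1.125.
- Adjusted: mean of the two order-specific means, SE = 0.5√(1/n₁ + 1/n₂), df = n − 2. At 8:7, SE = 0.259.

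Unadjusted results come from 200,000 simulated trials per setting. The two unadjusted power figures are for bias against and in favour of OT.

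| Orders | π (SD) | Bias (SD) | Type I error, unadjusted | Power, unadjusted | Power, adjusted |
|---|---|---|---|---|---|
| 8:7 | 0 | 0 | 0.05 | 0.821 | 0.815 |
| 8:7 | 0.25 | 0.017 | 0.044 | 0.79 / 0.82 | 0.815 |
| 8:7 | 0.5 | 0.033 | 0.030 | 0.71 / 0.78 | 0.815 |
| 8:7 | 0.75 | 0.05 | 0.017 | 0.58 / 0.71 | 0.815 |
| 9:6 | 0.5 | 0.10 | 0.041 | 0.62 / 0.85 | 0.801 |
| 10:5 | 0.5 | 0.167 | 0.063 | 0.54 / 0.90 | 0.771 |

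The high figures at 9:6 and 10:5 reflect bias toward OT, not real gain.

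**4. How unequal the orders may be.** Fifteen completers cannot split equally. From an exact 10:10 start, random loss of five leaves 9:6 or worse in 30% of trials and 10:5 in 3% (hypergeometric). If instead each sex has its own 20-code list with 10 per order, and about 10 codes are used (an assumption), the 20 participants split 12:8 or worse in 35% of draws and exactly 10:10 in 24%. After loss to 15, 10:5 or worse then occurs in about one trial in five.

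**5. Sex.** Sex main effects of 0, 0.5 and 1 SD leave the paired contrast unbiased, with simulated power of 0.822, 0.817 and 0.821.

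**The case against.** The strongest reply is that step 3 evaluates an analysis the plan does not state. The plan fits each session separately, uses pre-post change and has an untreated forearm as comparator. Read as a forearm-by-time contrast, that design removes level shifts and any change shift common to both forearms. This stands, and the figures in step 3 should be read only as the cost to a cross-session contrast. It does not dispose of the point: the aims ask about OT versus saline, the sample size is that of a paired contrast, and the stated criterion is a time effect, which a session effect on change does enter.

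It is also fair that the session effect is hypothetical and that at 0.25 SD the loss is small. The same-visit reading is inferred from the consent and session-timing text, since the design overview lists baseline calibration as a session of its own.

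Four stronger readings are tempting and not supported:
- Omitting sex does not bias the result or widen its error bars: its main effect cancels within a person, and Subject Population already plans a sex analysis.
- False positives are not generally inflated. At 8:7 and 9:6 the unadjusted test is conservative.
- Age and race/ethnicity need not be dropped. They are listed only as potential covariates.
- Adding session as a main effect to each separate per-session model is not enough. It leaves the time estimate and its standard error unchanged.

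**Conclusion.** The concern holds for session number. The plan randomises session order and then accounts for it in no model, while its aims need a comparison across sessions. With 15 completers near balance, the expected harm is lost power: from 0.815 adjusted to 0.71 or 0.78 at an assumed 0.5 SD session effect, and little or nothing at 0.25 SD. At 0.5 SD, bias is 0.10 SD at 9:6 and 0.17 SD at 10:5, with direction set by which order is larger and the sign of the session effect. Type I error exceeds 0.05 only at about 10:5 or worse. These sizes rest on the assumed session effect, a difference SD of 1, and a contrast of OT with saline in pre-post change that the plan implies but does not write down. The sex issue is one of consistency between two sections. This is a worthwhile, inexpensive improvement, not a fatal flaw.

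**What to change.** In Data Analyses and Interpretation:
- Fit one model across both sessions with treatment, time, forearm and their interactions, and name OT versus saline in pre-post change as the tested contrast for each aim.
- Include session number and session-by-time (equivalently, a session term in a model for change). If the tested contrast is also differenced against the control forearm, carry the session term to that same level.
- Include sex, to match the stratification and Subject Population. Age and race/ethnicity may stay.

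The session adjustment costs one degree of freedom in the model for change. With no session effect, power goes from 0.821 to 0.815 at 8:7, about 0.80 at 9:6 and 0.77 at 10:5. This part is SAP wording only.

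In Participant Randomization, generate each sex's order codes in small permuted blocks instead of one block of 20. With blocks of 4, for example, 10 codes per sex are two full blocks plus two codes. Those two codes match in 2 of the 6 possible arrangements, so the worst overall split is 12:8, with probability 1/3 × 1/3 × 1/2 = 1/18 (about 6%), against 35% above. This changes the pharmacy's list as well as the text, and does not prevent imbalance from later dropout.
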